9.4.5 Dose Administration

Study medication will be provided as either oral suspension or capsules. **Ganaxolone should be taken with a meal or snack**, whether oral suspension or capsules. Ganaxolone capsules should be administered with a glass of water or other liquid. Note that grapefruit and grapefruit juice are prohibited during the study.

Ganaxolone oral suspension will be administered through an oral dosing syringe administered or supervised by parents/guardians three times daily (TID), following the morning, noon, and evening meal or snack. Each dose should be separated by a minimum of 4 hours and a maximum of 8 hours. A missed dose of study medication may be taken

up to 4 hours before the next scheduled dose, otherwise, the missed dose should not be given.

Ganaxolone capsules will be administered two times daily (BID), following the morning and evening meal or snack. Each dose should be separated by a minimum of 8 hours and a maximum of 12 hours. A missed dose of medication may be taken up to 8 hours before the next dose, otherwise it should not be given. The capsules should be swallowed whole and not opened, crushed, or chewed.

Subjects and their parent or legal guardian will be informed about possible side effects from the study medication and cautioned to avoid quick postural changes, at least until they know how the study drug affects them. Subjects will be advised that the medication might affect mental alertness. They will also be cautioned that non-adherence to the dosing instructions (e.g. increasing the dose, taking the study medication doses too close together) could produce side effects.

9.4.6 Missing a Dose

Ganaxolone oral suspension: A missed dose of study medication may be taken up to 4 hours before the next scheduled dose, otherwise, the missed dose should not be given.

Ganaxolone capsules: A missed dose of medication may be taken up to 8 hours before the next dose, otherwise it should not be given.

Subjects and their parent or legal guardian should be instructed that if s/he misses two days in a row or more, the site should be contacted to determine whether any adjustment in study medication is needed.

9.4.7 Background AED medication:

Marketed medications indicated for the treatment of seizures are acceptable with the exception of **vigabatrin**, **tiagabine**, and **ezogabine**. **Felbamate** has restricted use. Chronic and rescue **benzodiazepine** use should be discussed with the Principal Investigator and Sponsor. Note:

Vigabatrin: Current use of vigabatrin (Sabril) is not permitted for the duration of the study due to its ophthalmologic toxicity, as well as prior use of vigabatrin without stable visual fields tested twice over the 12 months after the last dose of vigabatrin.

Felbamate: Felbamate (Felbatol) is permitted as a concomitant medication only if the subject has been on felbamate for at least 18 months and has stable AST/ALTs and hematology laboratory tests and is expected to remain constant throughout the study.

9.4.8 Concomitant Medications

A list of medications that are **inducers or inhibitors of CYP 3A4/5** and are not permitted during the study are included in the Appendix. Note that phenytoin and carbamazepine are permitted as background AEDs though they are moderate CYP 3A4 inducers. Finasteride is not permitted as it inhibits synthesis of endogenous allopregnanolone.

Generally, concomitant medications including non-prescription medication can be used if medically necessary and if the medication is not expected to interact with study medication nor to adversely impact the subject's ability to comply with protocol requirements. Concomitant medications prescribed by a physician other than the Investigator should be communicated to the Investigator promptly. The Investigator must make the decision to authorize the use of such a medication only after consideration of the clinical situation, the potential for masking symptoms of a more significant underlying event, and whether the use of the medication will compromise the outcome or validity of the clinical investigation. The Sponsor and the study Principal Investigator may be consulted for additional input. If medication is required, the name, strength, frequency, and reason for use will be recorded in source documents and the case report form (CRF).

9.4.9 Treatment Compliance

Subjects who are not compliant with study visits, study medications and seizure calendars may be removed from the study at the discretion of the Investigator or Sponsor.

9.5 Efficacy and Safety Variables

9.5.1 Calculation of Baseline

Baseline will be calculated from a maximum of 12 weeks' of seizure calendar data with a minimum of 4 weeks of data required, which should include contiguous retrospective ratings provided after signing informed consent. Acceptable retrospective daily seizure

data include a diary record of the frequency and type of seizures by day. Source data may include a seizure diary or calendar, recorded data from smart phones or other devices. Seizure clusters are to be identified, and the number of seizures in the daily cluster should be counted or given as best estimate.

9.5.2 Efficacy Assessments

Parent or legal guardian will record the type and number of seizures daily in the Subject Seizure Calendars that will be used for the primary analysis of efficacy.

The primary outcome measure is the percentage change in seizure (focal dyscognitive or focal convulsive) frequency per 28 days relative to baseline.

Secondary efficacy outcome measures include evaluation of inter-cluster interval; time to reach baseline number of seizures (per 28 days); seizure-free intervals; proportion of subjects with 50% improvement in number of seizures compared with baseline: and proportion of subjects whose inter-cluster interval increases by 50% or more. Additional measures may be added. Data will be analyzed for the ITT and Per Protocol populations if they differ.

The Clinical Global Impression of Improvement: Clinician (CGII-C) and Clinical Global Impression of Improvement: Patient/Caregiver (CGII-P) are secondary efficacy assessments.

9.5.3 Safety Assessments

Planned safety assessments include:

Neurological and physical examinations Clinical laboratory tests 12-lead ECG EEG

Vital signs including temperature, blood pressure, pulse rate, and weight AE monitoring: frequency, severity, duration, causality, outcome Columbia-Suicide Severity Rating Scale (CSSRS)

Clinical labs, vitals, EEG and ECG measurements may be repeated if needed to corroborate or refute abnormal findings. Both the original and replicate assessments should be recorded in the CRF.

See Appendix 1 Schedule of Study Events for timing of Safety Assessments.

Additional assessments may be conducted as considered appropriate.

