9.5.5.2 Visit 2 (Baseline; Week 0)

- Review medical history, background AEDs and other concomitant medications
- Review inclusion/exclusion criteria
- Collect and review seizure calendars
- VAS
- Administer Columbia Suicide Scale assessed for children 7 years and older
- Perform physical and neurological examinations
- Measure vital signs
- Draw blood sample for, hematology, chemistry, trough concomitant AED levels, and allopregnanolone, and related endogenous CNS-active steroids; obtain urine sample from subjects who are toilet trained for urinalysis and pregnancy test for WCBP.
- Dispense study medication and dosing instructions
- Instruct and provide study Subject Seizure Calendar
- EEG

- Screening and Baseline visits may be one visit if the seizure calendar data are sufficient.
- 9.5.5.3 Visit 3 (end of Week 2 + / 3 days)
 - Review background AEDs and other concomitant medications
 - Collect and review seizure calendars; provide new calendars
 - Administer Columbia Suicide Scale assessed for children 7 years and older
 - Perform follow-up physical and neurological examinations
 - Assess for adverse events
 - Measure vital signs
 - Collect bottles from prior visit study medication
 - Adjust dose if necessary
 - Dispense study medication
- 9.5.5.4 Visit 4 (end of Week 4 +/- 3 days)
 - Review background AEDs and other concomitant medications
 - Collect and review seizure calendars; provide new calendars
 - Complete CGII-Clinician Ratings
 - Instruct and collect CGII-Patient/Caregiver Ratings
 - Administer Columbia Suicide Scale assessed for children 7 years and older
 - Perform follow-up physical and neurological examinations
 - Assess for adverse events
 - Measure vital signs
 - 12-lead ECG
 - EEG
 - Collect bottles from prior visit study medication
 - Adjust dose if necessary
 - Dispense study medication
 - Urine Pregnancy Test for WCBP

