10.5.2 Evaluating and Recording of Adverse Events

At each visit all adverse events that are observed, elicited by the Investigator, or reported by the subject, will be recorded in the appropriate section of the CRF and evaluated by the Investigator.

Minimum information required for each AE includes type of event, duration (start and end dates), severity, seriousness, causality to study drug, action taken, and outcome.

Severity of AEs will be graded by the Investigator using the following criteria as guidelines:

1. Mild: Nuisance, barely noticeable.

2. Moderate: Uncomfortable, troublesome symptoms not significantly

interfering with daily activities or sleep.

3. Severe: Symptoms significantly interfere with daily activities or sleep.

The relationship of the AE to the study drug should be specified by the Investigator, using the following definitions:

1. Not Related: Concomitant illness, accident or event with no reasonable

association with study drug.

2. Unlikely Related: The event has little or no temporal sequence from administration

of the study drug, and/or a more likely alternative etiology exists.

3. Possibly Related: The event follows a reasonable temporal sequence from

administration of study drug but which could also be explained

by concurrent disease or other factors or medications

4. Probably Related: The event follows a reasonable temporal sequence from

administration of study drug, unlikely to be attributed

to concurrent disease or other factors or medications. A clinically

reasonable response may be observed if the study drug is

withdrawn or dose reduced.

5. Definitely Related: the event follows a reasonable temporal sequence from

administration of study drug and is definitive

pharmacologically; cannot to be attributed to concurrent disease or other factors or medications. A clinically reasonable response should be observed if the study drug is withdrawn or dose reduced.

When applicable, a syndrome ("flu syndrome") that describes a constellation of AEs should be recorded in the CRF in place of the individual AE terms (fever, sore throat, rhinitis).

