10.5.3 Reporting of Adverse Events

10.5.3.1 Serious Adverse Events

Any SAEs, including death due to any cause, which occurs to any subject who has signed Informed Consent (personally or by legal guardian) in this study or within 30 days following cessation of the last dose of treatment with the study drug, whether or not considered related to the investigational product, must be reported within 24 hours to the Sponsor or their designee. SAEs that occur more than 30 days after the last dose of study drug and are suspected to be related to study treatment should also be reported. All subjects with SAEs must be followed up for outcome.

SAEs can entered into the database and submitted to the sponsor.

SAE reporting numbers:

[contact]) (Medical)

[contact]

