13.2 Appendix 2: Schedule of Events – 26 Week Treatment Period

WEEK		0	2	4	8	17	26	
VISIT	V1 Screen ing	V2 Base line	V3 +/- 3 days	V4 +/- 3 days	V5 +/- 3 days	V6 +/- 7 days	V7 Final Visit ⁴ +/- 7 days	Unscheduled Visit or Dose Escalation Visit ⁶
			Screening &	& Diagnosis				
Informed consent	X							
Demographics	X							
Medical History	X	X						
Retrospective Seizure Diary Collection and Review	X							
Inclusion/Exclusion criteria	Х	X						
Background AEDs Review	X	X	X	X	X	X	X	X
Concomitant Med Review	X	X	X	X	X	X	X	X
			Safety As	sessments				
ECG	X			X				
Vital Signs ⁵	X	X	X	X	X	X	X	X
Physical Examination ¹	X	X	X	X	X	X	X	X
Neurological Examination ¹	X	X	X	X	X	X	X	X
Safety Labs (Blood ⁷ and Urine ²)		X			X		X	X
Urine Pregnancy Test (WCBP)		X		X	X	X	X	
Administer C-SSRS		X	X	X	X	X	X	X
EEG		X		X	X	X	X	
Review safety and record AEs			X	X	X	X	X	X
			Efficacy A	ssessments				
Instruct/ Provide Seizure Calendar	X	X	X	X	X	X	X	X
Subject Calendar Review	X	X	X	X	X	X	X	X
Complete CGII-C			_	X	X	X	X	
Instruct and Collect CGII-P				X	X	X	X	

Page 52 08 April 2016

WEEK		0	2	4	8	17	26	
VISIT	V1 Screen ing	V2 Base line	V3 +/- 3 days	V4 +/- 3 days	V5 +/- 3 days	V6 +/- 7 days	V7 Final Visit ⁴ +/- 7 days	Unscheduled Visit or Dose Escalation Visit ⁶
			Other A	ssessment	s			
VAS		X			X		X	
PK/PD Assessments								
Concomitant AED medications		X			X		X	
Study Drug Blood Samples					X		X	
Neurosteroid levels		X			X		X	
Study Medication								
Dispense Medication		X	X ³	X ³				
Collect bottles from prior visit study medication			X	X	X	X	X	X
Instruct on Down-titration							X ⁸	

- 1. Physical and neurological exam records performed at the same center within 60 days of screening visit may be used in place of screening exam. Visits 3, 4, 5 and 6 may be follow-up exams. Tanner Scores will be collected.
- 2. Obtain urine sample for those who are toilet trained.
- 3. Adjust dose if necessary.
- 4. This visit could also be an Early Termination visit. At this visit, investigator confirms if the subject qualifies for the 52 week extension, subjects must have completed all scheduled clinical study visits and have shown a minimum 35% improvement in mean seizure frequency per 28 days vs. baseline.
- 5. Vital signs including temperature, blood pressure, pulse, height and weight.

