7.1 ADVERSE EVENTS

Adverse events will be coded by SOC and Preferred Term using MedDRA®, version 16.0. The verbatim term will be included in the AE listings.

A treatment-emergent adverse event (TEAE) is defined as an AE that starts or worsens on or after the first dosing day of study drug. The AE analyses for the main 26-week open-label treatment period of the study will include AEs that start during that period and will not include AEs that start during the OLE period of the study; i.e. they will not include any AEs starting on or after the first dosing day of the OLE period. Pre-treatment emergent AEs will be summarized

by SOC and Preferred Term. Only TEAEs will be included in the other summary tables. Pre-treatment AEs and TEAEs will be presented in subject data listings.

The TEAEs will be summarized as the number of events and the number (percentage) of subjects with TEAEs. Subjects who report the same Preferred Term on multiple occasions will be counted once for the Preferred Term: under the highest severity (severe > moderate > mild) when summarized by severity and under the closest relationship (related > probably related > possible related > unlikely related > not related) to study drug when summarized by relationship.

Treatment related AEs are defined as those events recorded in the CRF as 'Related', 'Probably Related' or 'Possibly Related'; AEs recorded in the CRF as 'Unlikely Related' or 'Not Related' will be considered as not related to treatment. TEAEs with missing relationships will be considered as related.

If a subject reports multiple Preferred Terms for an SOC, the subject will be counted only once for that SOC. For the counting of events, all the Preferred Terms will be included in the counts, even when subjects have multiple Preferred Terms.

TEAEs will be summarized as below.

- An overview table, including number of events and subjects with
 - TEAEs
 - serious AEs (SAEs)
 - Treatment related TEAEs
 - TEAEs by severity
 - TEAEs leading to study discontinuation
 - TEAEs leading to death
- TEAEs by SOC and Preferred Term
- TEAEs by SOC, Preferred Term, and Severity
- Study drug related TEAEs by SOC, Preferred Term
- SAEs by SOC and Preferred Term
- TEAEs leading to study drug discontinuation by SOC and Preferred Term
- TEAEs by Preferred Term

All AE tables will be sorted by SOC and Preferred Term in decreasing frequency of the number of subjects in the combined cohorts. In cases of ties the sorting will be alphabetical.

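### The documents conflict on whether non-serious adverse events are sought before dosing: the schedules start AE review at Visit 3, while protocol 10.5.2 records AEs at each visit and SAP 7.1 tabulates pre-treatment AEs

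*Protocol*

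**What the plan says.** Protocol 9.5.3 names "AE monitoring: frequency, severity, duration, causality, outcome" among the planned safety assessments, gives no start visit, and refers to the schedule for timing. (It points to Appendix 1, which is the laboratory list; the schedule is in Appendix 2.)

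In Appendix 2 the row "Review safety and record AEs" is blank at Visits 1 and 2 and marked from Visit 3 onward. SAP Table 1 shows the same pattern. In the visit-by-visit lists of protocol 9.5.5, the item "Assess for adverse events" is absent at Visits 1 and 2 and first appears under Visit 3.

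Other sections read differently. Protocol 10.5.2 states: "At each visit all adverse events that are observed, elicited by the Investigator, or reported by the subject, will be recorded". It makes no exception for Visits 1 and 2. Protocol 10.5 asks the investigator to monitor for AEs throughout the study. Protocol 10.5.3.1 makes reportable any serious event "which occurs to any subject who has signed Informed Consent", so its clock starts at consent.

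SAP 7.1 assumes that pre-dose events are in the database: "Pre-treatment emergent AEs will be summarized" by system organ class (SOC) and Preferred Term, and "Pre-treatment AEs and TEAEs will be presented in subject data listings". It defines a treatment-emergent AE (TEAE) as "an AE that starts or worsens on or after the first dosing day of study drug".

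**The concern.** The study has no control arm, and safety and tolerability are its secondary objective. What is known about each child before the first dose is therefore a large part of the context for reading on-drug events. The protocol's introduction lists constipation and sleep difficulties among the features of CDKL5 disorder, so some background complaints are to be expected in that cohort whatever the drug does.

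A coordinator who works from the visit list or the schedule has no prompt to ask about AEs until the child is on drug. One who works from 10.5.2 would ask at Visits 1 and 2. Both would be following the protocol, yet they would supply different data to the same SAP table. Three things are at stake: whether the pre-treatment AE table can be interpreted, whether the worsening part of the TEAE definition can be applied, and how complete the onset dates are for events that straddle the first dose.

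**Working it through.** No published figure is involved, so the check sets the texts side by side and follows the date rule through.

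**Scheduled AE reviews (Appendix 2 and SAP Table 1)**
- Visits 1 and 2: 0 + 0 = 0.
- Visits 3, 4, 5, 6 and 7: 5, plus any unscheduled or dose-escalation visit.
- Pre-dose window: up to 12 weeks of charting after consent. It is about 0 where screening and baseline are one visit, which 9.5.5.2 allows.
- First scheduled question: end of Week 2, ± 3 days. Recall back to consent can then span up to 12 + 2 = 14 weeks.

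**Which text governs Visits 1 and 2?**
- Not sought: the Visit 1 and 2 lists, Appendix 2 and SAP Table 1.
- Sought: 10.5.2 (each visit, elicited events included) and 10.5 (throughout the study).
- Unclear: 10.5.1 ties an AE to the use of a drug, which leaves the status of a pre-dose non-serious event open. The synopsis speaks of spontaneous reports, which sits badly with elicitation in 10.5.2 but applies to every period.
- Serious events: covered from consent by 10.5.3.1, which works by event and not by visit. There is no conflict here.

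**Does late asking turn a background event into a TEAE?** Not by itself. Status follows the date of onset or worsening, not the visit of report. An event first mentioned at Visit 3 with a known pre-dose start, and no worsening, is pre-treatment.

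**Where dates are incomplete.** To determine treatment-emergent status, SAP 7.1 sets the start to the first dose date in three cases: the whole date is missing; only the year is known and it is the first-dose year; or the day is missing and the month and year are those of the first dose. If that start is later than the stop date, after any imputation of the stop date, the stop date replaces it. Take a first dose on the 20th of a month, and an event that truly began on the 8th:
- Full start date known: the 8th is before the 20th, so pre-treatment.
- Start known to the month only, event ongoing: start set to the 20th, so TEAE.
- Start known to the month only, stop known as the 10th: the 20th is later than the 10th, so the start becomes the 10th, and the event is pre-treatment.
- Start and stop both known to the month only, true end on the 10th: start set to the 20th, stop set to the last day of the month. The stop-date rule does not act, so TEAE.

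With a first dose on day d, any of the d − 1 earlier days of that month can be the true onset in the second and fourth cases (here 20 − 1 = 19 days). Asking first at Week 2, by recall, makes such partial dates more likely.

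**Worsening.** The TEAE definition includes worsening, but no AE severity grade is scheduled before dosing. Medical history is taken at Visit 1 and reviewed at Visit 2. SAP 4.2 summarizes clinically significant history by SOC and Preferred Term, and no severity grade for it is described.

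**The case against.** The strongest reply is that 10.5.2 and 10.5 already require AEs to be recorded at every visit, and serious events are reportable from consent. On that view the schedule merely omits a mark. This stands in part: a reader might infer that pre-dose events go unasked, but the documents support only that they disagree on the point.

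A reader might also infer that background symptoms will look drug-emergent simply because the first question comes at Visit 3. The onset test in SAP 7.1 rules that out. What remains is incomplete or misremembered dates, and worsening that cannot be checked.

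It can be said too that pre-dose documentation exists: history, concomitant medication, and physical and neurological examinations at Visits 1 and 2, with laboratory tests, EEG, the behaviour scale and, from age 7, the suicidality scale at Visit 2. That is fair, although none of it is a graded AE record.

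Nor is the pre-dose period the only scheduled look off drug, since Visit 11 is a post-drug follow-up with an AE check. It is a weak substitute. It falls at Week 82, 82 − 78 = 4 weeks after Visit 10, and down-titration may itself take up to 4 weeks. SAP Table 2 does not apply it to children who continue ganaxolone.

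Finally, one might put a number on the effect. If half of pre-dose events and all on-drug events were captured, equal true rates would show a ratio of 1/0.5 = 2; at 80% or 25% capture the ratio would be 1.25 or 4. No capture fraction is given in the documents. SAP 7.1 reports event counts and subject percentages, not rates, and plans no comparison of pre-dose with on-drug events. These ratios are therefore not findings.

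**Conclusion.** The conflict is real and can be seen from the text. The protocol visit lists and both schedules first place AE review at Visit 3, whereas 10.5.2 requires recording at each visit and SAP 7.1 tabulates pre-treatment AEs.

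For a site that follows the schedule, three consequences hold. Pre-treatment non-serious AEs would be under-ascertained. No graded pre-dose severity would be available for judging worsening. Some pre-dose events with incomplete start dates would be counted as TEAEs, except where a known stop date precedes dosing.

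The size of these effects cannot be derived from the documents. It depends on how many sites followed the schedule instead of 10.5.2, and on how many onset dates were incomplete; neither is stated. The documents do not support a claim that late reporting alone creates TEAEs, or that a particular inflation of the on-drug rate follows.

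One limit on the evidence: the SAP cites protocol Amendment 8.1, which is later than the supplied protocol of April 2016. SAP Table 1 still shows the Visit 3 start, but the Amendment 8.1 visit lists could not be checked.

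**What to change.** Add "Assess for adverse events", covering the time since consent, to protocol 9.5.5.2, and mark Visit 2 in the AE row of Appendix 2 and of SAP Table 1, so that all three agree with 10.5.2. This gives the planned pre-treatment table a systematic source, supplies a starting severity, and obtains onset dates closer to the event.

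The SAP describes enrolment and treatment in the past tense, and its section 11 says the remaining cohorts were analyzed only after the main and extension periods had completed. A new visit item cannot recover data already collected. For those data, label the SAP 7.1 pre-treatment AE table as not systematically elicited and as covering unequal windows of about 0 to 12 weeks, or drop the table.

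Pre-treatment and on-treatment rates per subject-time could be shown side by side, but that is an optional preference. With about 10 children per cohort and some windows near zero, it would carry little weight.

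The cost is one line in a visit list, one mark in each of two tables, a few extra CRF entries, and a footnote for existing data. Children whose Visits 1 and 2 are combined would still add no pre-dose time.
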